An independent Clinical Events Committee (CEC) will be established for this study to review case information on serious cardiovascular (CV) events (myocardial infarction, stroke, death, hospitalization for angina, hospitalization for transient ischemic attack (TIA). The operations, processes, and definitions to be employed by the committee will be defined in the CEC charter.

Three primary database locks (DBLs) are planned for reporting of the results:

- The first DBL for the primary analysis will occur after all subjects have completed the Week 52 visit assessments in Part A or have withdrawn prematurely from the study. Treatment-level data will be unblinded to Sponsor personnel.
- The second DBL for the 6-month follow-up will occur after all subjects have completed the Week 24 visit in Part B, or have withdrawn prematurely from the study. The data from subjects undergoing the 16-week follow-up assessments at the end of Part A will also be included and will potentially comprise a separate data set/report if applicable.

- The third planned DBL will occur after all subjects have completed the last visit in Part B, or have withdrawn prematurely from the study. The Part B DBL will include the data from all visits associated with Part B of the study, including the 16-week follow-up assessments of Part B if applicable.

The utility of US in monitoring disease activity in GCA will be explored in a cohort of subjects from select centers who have qualified as US imaging centers. Longitudinal changes in vascular inflammation of the temporal and axillary arteries will be assessed and changes will also be correlated with clinical markers. Additional details on the exploratory US imaging cohort are contained in Section 7.9 and Appendix 8.

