#### **7.5.1.3. Follow-up of AEs and SAEs**

After the initial AE/SAE report, the investigator is required to proactively follow each subject at subsequent visits/contacts. All SAEs, and non-serious AEs of special interest (as defined in Section [4.6.1](#)) will be followed until resolution, until the condition stabilizes, until the event is otherwise explained, or until the subject is lost to follow-up (as defined in Section [5.4](#)). Further information on follow-up procedures is given in [Appendix 4](#).

Other AEs of special interest not defined in Section [4.6.1](#) are injection site reactions, total or partial blindness, limb claudication, and scalp or tongue necrosis. In addition, severe disease flares, including hospitalizations will be monitored.

Other AEs of special interest for sirukumab are hematologic laboratory abnormalities (decreases in neutrophils and platelets), hepatobiliary laboratory abnormalities, lipid parameter abnormalities, serious CV events, infections, malignancies, and gastrointestinal perforations.

All initial reports of cardiovascular AEs (myocardial infarction, stroke, death, hospitalization for angina, hospitalization for TIA), newly identified malignancies, active TB, hepatobiliary abnormalities (as defined below), and gastrointestinal perforations

must be reported to the Sponsor by the investigational staff within 24 hours of their knowledge of the event even if these events do not meet the definition of an SAE.

Corticosteroid-related AEs such as diabetes mellitus, osteoporosis, fractures, infection, glaucoma, and cataracts among others will be evaluated in relation to steroid exposure and baseline risk. Since subjects participating in this study may be receiving high doses of prednisone for a prolonged period, investigators should consider implementation of the American College of Rheumatology recommendations for the prevention and treatment of glucocorticoid-induced osteoporosis (Grossman, 2010). A summary of these recommendations is included in Section 12.5, Appendix 5. Investigators should also consider whether their subjects may benefit from other approaches for minimizing corticosteroid-related AEs, such as the prophylactic use of proton pump inhibitors for gastroprotection.

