#### **7.5.1.4. Cardiovascular and Death Events**

For any cardiovascular events detailed in Appendix 4 and all deaths, whether or not they are considered SAEs, specific Cardiovascular (CV) and Death sections of the CRF will be required to be completed. These sections include questions regarding CV (including sudden cardiac death) and non-CV death.

The CV CRFs are presented as queries in response to reporting of certain CV MedDRA terms. The CV information should be recorded in the specific cardiovascular section of the CRF within one week of receipt of a CV Event data query prompting its completion.

The Death CRF is provided immediately after the occurrence or outcome of death is reported. Initial and follow-up reports regarding death must be completed within one week of when the death is reported.

In the sirukumab clinical programs, significant changes in lipid laboratory parameters have been observed, as with other agents that block IL-6. The clinical significance of these changes is not known. Nonetheless, serious CV events are considered AEs of special interest and will be closely monitored in the sirukumab program. In order to fully understand CV events in this study, Major Adverse Cardiovascular Events (MACE), defined as myocardial infarction, stroke, death, hospitalization for unstable angina, and hospitalization for TIA, will be collected and prospectively adjudicated by an external CEC. The CEC is an independent committee composed of external specialists, blinded to treatment assignment, who will be commissioned to review case information on serious CV events. This will allow external review of cases and determination of diagnosis prior to analysis.

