### **Other Events of Interest**

Sirukumab, by its mechanism of action as an IL-6 inhibitor, would be expected to have some properties of immunosuppression. Increased susceptibility to infections is an identified risk of sirukumab. Serious, life-threatening infections such as septic shock, some of which have been fatal, have occurred in subjects receiving sirukumab. IL-6 deficient mice have been found to be susceptible to infections with *Listeria monocytogenes*, *Toxoplasma gondii*, and *Candida albicans*. [Dalrymple, 1995; Romani, 1996; Suzuki, 1997]. In addition, as an IL-6 inhibitor, sirukumab may have some effect on the risk of malignancy by affecting immune surveillance. Further, gastrointestinal perforations have been reported with another anti-IL-6 agent [ACTEMRA Prescribing Information, 2011] and with sirukumab. Please refer to Table 4.6.1 and the Investigator Brochure for additional information.

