9.1.8. Adverse Events of Special Interest

The identification, classification and adjudication of adverse events of special interest (AESI) will occur in a blinded fashion quarterly by the GSK medical monitor. The final adjudication will take place prior to database releases and will be performed for reporting purposes.

Where available, AEs will have SMQ flags assigned to help the adjudication process at GSK. These flags will help but not over-rule individual event adjudication performed by GSK. All AE terms will be adjudicated at the subject level by GSK, in order to identify any events that are AESI as defined by the protocol as well as to assign each AESI category which will support later tabulation.

The groups of adverse events of special interest are defined below:

- Gastrointestinal perforation
- Diverticulitis
- Tuberculosis activation
- Serious/opportunistic infections

- Hypersensitivity
- Cytopenias
- Serious cardiovascular events
 - Major Adverse Cardiac Events (MACE) adjudicated by the CEC
 - MACE
- Malignancies
- Injection site reactions
- Severe flares including hospitalizations
 - Total/partial blindness
 - Limb claudication
 - Scalp or tongue necrosis
- Lipid increases
- Liver function test abnormalities
- Corticosteroid-related AE

An overall summary of AESIs will be presented summarizing numbers and percentages of subjects with events within each of the above categories as well as by SOC and PT.

Further details will be provided in summaries of each AESI separately. The summary of event characteristics will also be provided, including number of subjects with at least one event, number of events, the event characteristics (i.e. seriousness, relationship to study drug, severity and if the event was fatal or not), the number of occurrences, the outcome, the maximum intensity and the action taken. The worst case approach will be applied at subject level for the event outcome and the action taken, (i.e. a subject will only be counted once as the worst case from all of the events that that subject had). In addition, onset and duration of the first occurrences for each type of events will be summarized.

Time to onset of first AESI will be displayed and calculated as:

$$\text{Date of onset of first AESI} - \text{Date of first SC IP date} + 1 \text{ day}$$

Duration of first AESI will be displayed and calculated as:

$$\text{End date of first AESI} - \text{Start date of first AESI} + 1 \text{ day}$$

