The proportions of subjects with AESIs and relative risks for the six comparisons will be summarized in a table. This will be done using the RELRISK option of the table statement of the SAS PROC FREQ procedure.

A supportive listing of all AESI will be presented.

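### Infections as a group get no AESI rate or between-arm comparison, and the only planned safety contrast, a relative risk, cannot be estimated when the placebo arm has no event

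*SAP*

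**What the plan says.** **Infections.** SAP 9.1.8 has each adverse event adjudicated against the protocol's definition of an AESI and then assigned to a listed group. Apart from tuberculosis activation, the only group named for infection is "Serious/opportunistic infections". Protocol 7.5.1.3 gives a list of AESIs for sirukumab that ends with "lipid parameter abnormalities, serious CV events, infections, malignancies, and gastrointestinal perforations". Protocol 7.5.1.5 adds that "Increased susceptibility to infections is an identified risk of sirukumab". The same section 7.5.1.3 also refers to AESIs as defined in section 4.6.1, where the risk row covers serious and opportunistic infections only.

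**Rates and comparisons.** SAP 9.1.1 gives exposure-adjusted incidence with exact Poisson intervals for three sets of events: AESIs, SAEs and fatal SAEs. It gives proportions and relative risks, for six comparisons, for common AEs, defined as those above 5% in any arm and summarised by preferred term. SAP 9.1.8 gives proportions and relative risks for AESIs, again for six comparisons: "This will be done using the RELRISK option of the table statement of the SAS PROC FREQ procedure". Neither section states a zero-event rule, a risk difference or an interval method.

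**MACE.** Protocol 7.5.1.4 has MACE "defined as myocardial infarction, stroke, death, hospitalization for unstable angina, and hospitalization for TIA". Protocol 4.1 lists, among the events for the Clinical Events Committee (CEC), "hospitalization for angina, hospitalization for transient ischemic attack (TIA"), without the word unstable. Sections 7.5.1.3 and 10.8 also omit it. SAP 9.1.8 has two MACE rows and defines neither.

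**The concern.** After termination the SAP runs no statistical analysis of efficacy (1.1, 3.2). The relative risks in 9.1.1 and 9.1.8 are the only between-arm estimates in it, so what they cover and whether they can be computed decides how much comparative information the trial yields.

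Two gaps follow. An identified risk of the drug is not compared as a group: infections spread over many preferred terms are compared one term at a time, and only above the 5% threshold. And a ratio with one placebo arm in the denominator fails when that arm has no event, which is plausible for rare AESI categories.

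**Working it through.** **Step 1. Where a non-serious, non-opportunistic infection appears.**

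| Output | Included? | All infections as a group? |
|---|---|---|
| TEAE table by SOC and PT (SAP 9.1.1) | Yes | By-arm count and percentage in the SOC row; no contrast |
| Common-AE relative risks (9.1.1) | If its term exceeds 5% in an arm | No, term by term |
| Exposure-adjusted rates (9.1.1) | Only if adjudicated to an AESI group | No |
| AESI relative risks (9.1.8) | Only if adjudicated to an AESI group | No |

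The one AESI group that might take such an event is corticosteroid-related AE, because protocol 7.5.1.3 gives infection as an example of one. There it would be mixed with other steroid toxicity.

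**Step 2. Arm sizes and contrasts.** Protocol 4.2.1 plans 204 subjects at 3:3:2:2:2. So 204 × 3/12 = 51 in Arms A and B, and 204 × 2/12 = 34 in Arms C, D and E, which matches the stated sizes. SAP 9.1.8 does not list its six comparisons. SAP 2.1.1 and 2.1.2 give exactly six (A, B and C, each against D and E), with no pooling of placebo arms.

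**Step 3. When the ratio fails.** With a events among n1 on sirukumab and c among n0 on placebo, RR = (a/n1)/(c/n0). At c = 0 the denominator is zero. For true risk p, P(c = 0) = (1 − p)^n0. The documents give no AESI rates and no arm sizes at termination (SAP 4.1 says only that the sample size will be the number randomized by then), so p and the smaller n0 are assumptions.

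| Assumed risk p | n0 = 34 (planned) | n0 = 20 (assumed) | n0 = 10 (assumed) |
|---|---|---|---|
| 1% | 71% | 82% | 90% |
| 2% | 50% | 67% | 82% |
| 3% | 36% | 54% | 74% |
| 5% | 17.5% | 36% | 60% |
| 10% | 2.8% | 12% | 35% |

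The chance that at least one of Arms D and E has no event, at 34 each with equal risk, is 1 − [1 − (1 − p)^34]². That is 92%, 75%, 32% and 5.5% at 1%, 2%, 5% and 10%.

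**Step 4. The common-AE table is affected too.** A term qualifies if any one arm exceeds 5%. At planned sizes 3/51 = 5.9% qualifies, so 3/51 against 0/34 enters the table and has no ratio.

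**Step 5. A measure that survives.** Newcombe's interval for the risk difference combines the two Wilson score intervals. For 3/51 the Wilson limits are 2.0% and 15.9%; for 0/34 they are 0 and 10.2%. The difference is 5.9%. The lower limit is 5.9 − √[(5.9 − 2.0)² + 10.2²], about −5.0%. The upper limit is 5.9 + (15.9 − 5.9) = 15.9%. In the same way, 1/51 against 0/34 gives 2.0% (−8.3% to 10.3%), and 5/51 against 0/34 gives 9.8% (−1.8% to 21.0%). The relative risk is undefined in all three cases.

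**The case against.** The SAP did not invent its label. Protocol 4.6.1 uses the same one, and 7.5.1.3 points to 4.6.1. This stands: the SAP follows one of two protocol lists, so the fault is an unreconciled protocol conflict rather than a plain SAP omission.

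Non-serious infections are also not lost. A reader might infer that the plan leaves them out altogether, and the documents do not support that. Each subject is counted once at every level of the SOC and PT table, non-serious opportunistic infections fit the SAP group, and tuberculosis has its own. What is missing is a rate and a contrast for infections together.

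On the ratio, a reader might infer that rare risks return an empty cell, or that an undefined ratio is the usual result. Neither is supported. The per-arm proportions and exact Poisson rates exist at zero events, and at the planned size the ratio fails in only 17.5% of cases at a 5% risk and 2.8% at 10%. These outputs are descriptive, with no formal safety test. That lowers the stakes, but a descriptive contrast still has to be computable to be of use.

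On MACE, a reader might infer that deaths from infection contaminate the cardiovascular category and that MACE should count cardiovascular death only. The documents do not settle this. The CEC determines the diagnosis before analysis under a charter that is not among them, and narrowing the death component would change the protocol's definition. Fatal events are already shown separately in SAP 9.1.1, 9.1.4 and 9.1.7. The angina mismatch may be no more than a review list that is broader than the endpoint.

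**Conclusion.** The point holds in two limited parts. First, infections taken together have no exposure-adjusted rate and no between-arm comparison, although one protocol list names them without a qualifier as an AESI and the protocol calls them an identified risk. It would go too far to call them the most frequent risk, because neither document gives event frequencies.

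Second, the only between-arm safety measure is lost whenever the chosen placebo arm has no event. At the planned 34 the chance is even or greater at risks of 2% or less, about one in three at 3%, and small at 10%; it rises if termination left smaller arms. These figures rest on assumed risks and, below 34, on assumed arm sizes. Both gaps should be closed before the safety tables are produced. On MACE, all that is supported is that its wording should be made consistent.

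**What to change.** 1. Reconcile protocol 7.5.1.3, protocol 4.6.1 and SAP 9.1.8 on whether the AESI is all infections or only serious and opportunistic ones. Keep the existing group and add an all-infections row with the same exposure-adjusted rate and comparison outputs.
2. In SAP 9.1.1 and 9.1.8, report the risk difference with a score or exact 95% CI beside the relative risk, and say that the ratio will be shown as not estimable when the placebo arm has no event.
3. State one MACE definition throughout, in line with the CEC charter, settling angina or unstable angina. Leave the death component as the protocol defines it.

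The cost is SAP wording, standard procedure options and a few more table rows. The events are already MedDRA-coded, so no new data are needed.

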GSK	GlaxoSmithKline
HAQ-DI	Health Assessment Questionnaire – Disability Index
ICH E9	International Council for Harmonization Efficacy guideline 9
IDMC	Independent Data Monitoring Committee
IFN	Interferon
IL	Interleukin
IP	Investigational Product
ITT	Intent-to-Treat
MACE	Major Adverse Cardiac Events

MCS	Mental Component Summary
MedDRA	Medical Dictionary for Regulatory Activities
MMRM	Mixed Model for Repeated Measures
NRS	Numeric Rating Scale
P1NP	Procollagen Type 1 N-propeptide
PCI	Potential Clinical Importance
PCS	Physical Component Summary
PD	Pharmacodynamics
PGIC	Patient Global Impression of Change
PH	Proportional Hazards
PK	Pharmacokinetics
PMR	Polymyalgia Rheumatica
PP	Per Protocol
PT	Preferred Term
PhGA	Physician Global Assessment of disease activity
PtGA	Patient Global Assessment of disease activity
PRO	Patient-Reported Outcomes
q2w	Every 2 weeks
q4w	Every 4 weeks
SAE	Serious Adverse Event
SAP	Statistical Analysis Plan
SAS	Statistical Analysis System
SC	Subcutaneous
SD	Standard Deviation
SE	Standard Error
SIQ	Steroid Impact Questionnaire
SF-36v2	36-item Short Form health survey version 2
SMQ	Standardized MedDRA Query
SOC	System Organ Class
TEAE	Treatment-Emergent Adverse Event
TEAESI	Treatment-Emergent Adverse Event of Special Interest

US	Ultrasound
VAS	Visual Analogue Scale

1. Introduction

Sirukumab is a human anti-interleukin (IL)-6 immunoglobulin G1 (IgG1) kappa monoclonal antibody with a high affinity and specificity for binding to the human IL-6 molecule that is being developed for the treatment of giant cell arteritis (GCA).

Multiple lines of evidence support a role for IL-6 in the pathophysiology of GCA. Sirukumab may have therapeutic benefit in the treatment of GCA by interruption of multiple pathogenic pathways. The purpose of this study is to evaluate the efficacy and safety of sirukumab to characterize the benefit-to-risk profile of sirukumab in the treatment of active GCA.

This Statistical Analysis Plan (SAP) is based on the protocol version 3.0 dated of 17th November 2016. This SAP contains definitions of analysis sets, derived variables and statistical methods for the analyses of efficacy and safety endpoints.

[Section 4](#) to [Section 10](#) focus on Part A of this study. Specific derivations for Part B will be presented in [Section 11](#).

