 - If the year is the same as first SC IP dose in Part A and the end date (after any imputation) is prior to first SC IP dose in Part A, then assume the end date for the start date.

Missing stop/end dates (where UK and UKN indicate unknown or missing day and month, respectively):

- UK-*MMM*-*YYYY*: Assume the last day of the month.
- DD-UKN-*YYYY*/UK-UKN-*YYYY*: Assume 31-DEC-*YYYY*.

In case of the death of the patients and the imputed end date is after the date of death, the stop/end date will be imputed as the date of death.

Completely missing dates will not be imputed.

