Only demographic and baseline characteristic as well as Safety will be displayed for Part B. All demographic and baseline characteristic as well as Safety summaries produced for Part A will be produced for Part B. Part B outputs will be displayed using the same general layout of Part A outputs, using the same Part A group as the treatment groups.

Each output will be split using a by-line which will contain information on Part B:

- “Never Received OL Sirukumab during Part B” will include all subjects who did not take a dose of Received OL Sirukumab during Part B.
- “Received at Least 1 Dose of OL Sirukumab during Part B” will include all subjects who took at least one dose of OL Sirukumab during Part B.

The Baseline for Part B will be the last measurement done up to and including the Week 52 visit date of Part A.

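### AESI duration is summarised from resolved events only, and the Part B repeat of the AESI onset table has no stated starting date

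*SAP*

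**What the plan says.** SAP 9.1.8 plans, for each AESI category, that "onset and duration of the first occurrences for each type of events will be summarized". Two formulas follow.

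- Onset: "Time to onset of first AESI will be displayed and calculated as" the onset date minus the "Date of first SC IP date", plus one day. No study part is named.
- Duration: "Duration of first AESI will be displayed and calculated as" the "End date of first AESI" minus its start date, plus one day.

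On dates, SAP 4.6.4 moves a partial end date to the end of the month or to 31 December, then adds: "Completely missing dates will not be imputed". Neither section says what to do with an event that has not ended.

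On Part B, SAP 1 limits Sections 4 to 10 to Part A and sends the rest to Section 11: "Specific derivations for Part B will be presented in" that section. Section 11 opens with "All demographic and baseline characteristic as well as Safety summaries produced for Part A will be produced for Part B", so the AESI table is repeated. Section 11 then gives Part B dates for exposure (11.2), concomitant medication (11.3) and the adverse event period (11.5). It gives none for AESI onset, and it does not say whether the first AESI means first in Part B or first in the study.

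**The concern.** Onset and duration are the two timing descriptions a reader will take from the AESI tables.

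For duration, the formula removes exactly the events that last longest. The SAP list includes malignancies and corticosteroid-related events, and Protocol 7.5.1.3 gives diabetes, osteoporosis, glaucoma and cataracts as examples of the latter. Many of these would be expected to be ongoing at last contact, all the more because the study was terminated on 10 October 2017. A median over resolved events then describes a selected subset without saying so.

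For Part B onset, a subject from Arm D or E who takes open-label sirukumab meets the drug for the first time in Part B. If the clock starts at the first Part A injection, which was placebo, an early event on sirukumab is tabulated as a late one. Two programmers working from this SAP could also choose different anchors and produce figures a year or more apart.

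**Working it through.** The SAP states no figure for AESI onset or duration, so there is nothing to reproduce. The checks below show how large each effect could be.

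**1. Duration.** The inputs are assumptions, because the documents give no AESI durations:

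- Durations are exponential with median *m*, so λ = ln 2 / *m*.
- Observation after onset is uniform on *a* to *b* days. One case is 0 to 364. The other is 112 to 476, which guarantees every event the 16-week safety follow-up of SAP 1.1 (112 days; 364 + 112 = 476).

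Share still ongoing, hence dropped = (e^(−λa) − e^(−λb)) / (λ(b − a)).

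For *m* = 90, λ = 0.00770:

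- 0 to 364: (1 − 0.0606) / 2.803 = 0.335.
- 112 to 476: (0.4221 − 0.0256) / 2.803 = 0.141.

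For *m* = 180, λ = 0.00385:

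- 0 to 364: (1 − 0.2462) / 1.402 = 0.538.
- 112 to 476: (0.6497 − 0.1599) / 1.402 = 0.349.

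The resolved-only median is the median of the density proportional to λe^(−λt) × P(follow-up ≥ t), solved numerically.

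| True median | Follow-up | Dropped | Resolved-only median |
|---|---|---|---|
| 90 d | 0–364 d | 34% | 58 d |
| 90 d | 112–476 d | 14% | 73 d |
| 180 d | 0–364 d | 54% | 77 d |
| 180 d | 112–476 d | 35% | 102 d |

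For short events the effect is small. With follow-up of 112 to 476 days, a true median of about 21 days (mean 30) loses 0.2% of events and the median does not move materially.

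Some durations move the other way. A missing end day is set to the last of the month (up to +30 days), and a missing end month to 31 December (up to +364 days in a non-leap year).

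**2. Part B onset.** Inputs: Part A lasts 52 weeks, and open-label sirukumab may start from Part B entry through Part B Week 52 (SAP 3.1 and 3.3).

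Shift if the Part A date is used = (52 + Part B week of open-label start) × 7 days.

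| Open-label start | Shift | Event on open-label day 28 is tabulated at |
|---|---|---|
| Part B Week 0 | 364 d | day 392 |
| Part B Week 24 | 532 d | day 560 |
| Part B Week 52 | 728 d | day 756 |

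Reaching 728 days by the termination date requires a first dose by 13 October 2015 (10 October 2017 minus 728 days). The documents give no first-dose date.

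**3. Which anchor the text implies.** SAP 4.5 counts study day from the first Part A dose, and SAP 11.2 and 11.5 name Part B expressly when they mean a Part B dose. The unqualified wording in 9.1.8 therefore reads most naturally as the first Part A dose. It remains an inference, because 9.1.8 is a Part A section and Section 11 is silent.

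**The case against.** Several stronger readings are tempting, and the documents do not support them.

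- *The SAP counts Part B onset from the first Part A dose.* It does not say so. The anchor is undefined, and the Part A dose is its literal reading.
- *AESI timing is wrong throughout.* Part A onset is correctly anchored. For Arms A to C the first Part A dose is also the first sirukumab dose, so it stays a valid origin for time since first exposure in Part B.
- *Onset is overstated by one to two years.* The two-year end is a design limit. SAP 1.1 describes few subjects completing Week 52, so few if any could have reached it.
- *All durations are biased short.* Short events are hardly affected, and imputing partial end dates lengthens some durations.
- *Lasting toxicity is hidden.* The same table reports event counts and outcome, all AESIs are listed, and SAP 4 has continuous summaries show the number of subjects.

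The best defence on size is follow-up. Protocol 7.5.1.3 follows serious events and the AESIs of its Section 4.6.1 until they resolve, stabilise or are otherwise explained, or the subject is lost. SAP 1.1 requires a 16-week safety visit and allows later visits for an ongoing event. This is a fair reason to prefer the 112 to 476 day rows, but it does not remove the bias. A stabilised event need not have an end date, and SAP 1.1 withdraws from the 16-week follow-up any subject who starts an anti-IL-6, another biologic or an investigational agent. The outcome row takes the worst case over all of a subject's events, so it does not show how many first events lack a duration.

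On attribution, SAP 11.5 splits Part B events by any open-label use and by whether they fall within 16 weeks of drug. An early open-label reaction would be classed as exposed. That limits the harm, but it gives no time to onset.

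**Conclusion.** Both gaps are real, and both concern descriptive safety tables that feed no test or decision rule.

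Duration is the firmer point. Ongoing first AESIs drop out, and the summary is biased short for long-lasting types. Under the exponential illustration, a 90-day median shows as about 58 to 73 days and a 180-day median as about 77 to 102 days. Those figures rest on assumed durations and follow-up, and on an ongoing event carrying no end date. The direction for long-lasting events does not depend on the exponential form, but imputed partial dates could offset some of it.

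The Part B onset point is an omission with a narrow reach. It matters for Arm D and E subjects who start open-label sirukumab. If the literal reading is programmed, their onset relative to first sirukumab is shifted by at least about 364 days, with a design maximum of 728 days.

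**What to change.** **SAP 9.1.8, duration.** Summarise the duration of first AESI by Kaplan-Meier, censoring ongoing events at last contact, and print the number ongoing beside each median. The SAP already uses Kaplan-Meier with censoring for time to flare (8.2.3 and 11.4.1).

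**SAP 11.5, Part B onset.**

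- Arms D and E: for events after the first open-label dose, count onset from that dose.
- Arms A to C: keep time from the first Part A sirukumab dose, and add time from the first open-label dose where one was given.
- Do not restart the clock at Part A Week 52 for Arms A to C subjects without open-label drug, because that would discard up to a year of earlier sirukumab exposure.
- State whether the first AESI in the Part B table is the first in Part B or the first in the study.

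The cost is a few lines of SAP text and a small change to one table's programming, with no new data. The drawback is that some median durations will be reported as not reached, which is the accurate answer when most events of a type are ongoing.
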